### **7.5.3 Laboratory Data**

Laboratory variables will be examined using mean change in value from baseline to scheduled time points. The baseline value of a variable is defined as the last value obtained on or before the date and time of the first dose of CB-839 or nivolumab. Proportion of patients with laboratory measurement outside the normal range and by NCI CTCAE v4.03 grade will be summarized.

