#### 6.4 Inclusion Criteria

1. Patients must have a histological or cytological diagnosis of metastatic cancer or locally advanced cancer that is not amenable to local therapy. Additional criteria specific to different Cohorts of the study are provided below.
2. Ability to provide written informed consent in accordance with federal, local, and institutional guidelines
3. Age  $\geq$  18 years
4. Eastern Cooperative Oncology Group (ECOG) Performance Status of 0-1
5. Life Expectancy of at least 3 mo
6. Patient must have adequate organ function as indicated by the following laboratory values:

Test	Value
Absolute neutrophil count (ANC)	$\geq 1,500$ /mcL
Total white blood cell (WBC) count	$\geq 2,000$ /mm 
Platelets	$\geq 100,000$ / mcL
Hemoglobin	$\geq 9$ g/dL
Serum creatinine	$\leq 1.5$ X upper limit of normal (ULN)
Serum total bilirubin	$\leq 1.5$ X ULN OR
Direct bilirubin (for patients with Gilbert Syndrome and total bilirubin levels $>1.5$ ULN)	$\leq$ ULN
AST (SGOT) and ALT (SGPT)	$\leq 2.5$ X ULN

International Normalized Ratio (INR) or Prothrombin Time (PT)	$\leq 1.5 \times \text{ULN}^*$
Activated Partial Thromboplastin Time (aPTT)	$\leq 1.5 \times \text{ULN}$

\* Does not apply to patients receiving therapeutic warfarin

7. Measurable Disease: At least one tumor lesion/lymph node that meets the RECIST v1.1 criteria for measurable disease
8. Female patients of childbearing potential must have a negative serum or urine pregnancy test within 3 days prior to the first dose of study drug and agree to use dual methods of contraception if sexually active during the study and for a minimum of 3 mo following the last dose of study drug. Post-menopausal females (> 45 years old and without menses for > 1 year) and surgically sterilized females are exempt from these requirements. Male patients must use an effective barrier method of contraception during the study and for a minimum of 3 mo following the last dose of study drug if sexually active with a female of childbearing potential.
9. Resolution of all treatment-related toxicities from any previous cancer therapy (including radiation and surgery) to  $\leq$  Grade 1 or to values within those required for eligibility on this study prior to the first dose of study treatment.
  - a. Exceptions include alopecia, anemia, or endocrinopathies managed by hormone replacement

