## 16.6 Safety Analysis

Safety variables to be analyzed by tumor type are AEs, laboratory test results (hematology, coagulation, serum chemistry, and urinalysis), ECG, weight, and vital signs.

Adverse event terms recorded on the eCRFs will be mapped to preferred terms using the most recent version of the Medical Dictionary for Drug Regulatory Activities (MedDRA®). All AEs will be summarized according to the system organ class and preferred term within the organ class. Adverse events will be tallied for overall frequency (number and percentage of patients), worst reported severity, and relationship to study drug for each preferred term per patient. Serious adverse events will be similarly summarized. Listings of deaths, SAEs, and AEs leading to early termination of study treatment or premature withdrawal from study will also be provided.

Laboratory variables will be examined using mean change in value from baseline to scheduled time points. The baseline value of a variable is defined as the last value obtained on or before the date and time of the first dose of CB-839 or nivolumab.

ECG, weight, and vital signs will also be summarized by changes from baseline to scheduled time points using descriptive statistics.

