### **7.5.2 Adverse Events**

Verbatim description of adverse events will be coded to System Organ Class (SOC) and Preferred Term (PT) using the Medical Dictionary for Regulatory Activities (MedDRA) and graded by the investigator according to NCI CTCAE v4.03. Treatment-emergent AEs (TEAEs) are defined as AEs started or worsened on or after first dose and will be tabulated. The number and proportion of patients reporting a given TEAE will be tabulated according to the worst severity grade reported. Separate tables will be constructed for a) all reported TEAE's, b) serious TEAEs (treatment-emergent SAEs), c) severe TEAEs (Grade  $\geq 3$ ), and d) TEAE's leading to permanent discontinuation or interruption of study treatments. The above tables will also be presented for TEAEs judged to be related to either study treatment.

Multiple occurrences of the same event will be counted once at the maximum grade. In order to accurately summarize the true TEAE rate, all TEAE summaries will not count grade 5 events for patients who died due to progressive disease.

All listings of adverse events will include both TEAEs and non-TEAEs.

Deaths reported during the study treatment period and the follow-up period after treatment completion/discontinuation will be listed and summarized by cause.

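### SAP 7.5.3 sets no baseline condition on its out-of-range and CTCAE-grade laboratory summary, so pre-existing abnormalities cannot be separated from new or worsened ones

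*SAP*

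**What the plan says.** SAP 7.5.3 (Laboratory Data) opens with mean change from baseline at scheduled time points and then defines baseline: "The baseline value of a variable is defined as the last value obtained on or before the date and time of the first dose of" either study drug. The categorical summary follows: "Proportion of patients with laboratory measurement outside the normal range and by NCI CTCAE v4.03 grade will be summarized". That sentence does not use the baseline just defined. It does not say which visits count, whether the worst value per patient is taken, or whether baseline is shown alongside.

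Protocol 16.6 (Safety Analysis) plans only the continuous summary: "Laboratory variables will be examined using mean change in value from baseline to scheduled time points". Neither document plans a shift table.

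Protocol 6.4 (Inclusion Criteria), item 6, admits AST and ALT up to 2.5 times ULN, creatinine and total bilirubin up to 1.5 times ULN (higher total bilirubin in Gilbert syndrome if direct bilirubin is normal), and hemoglobin of 9 g/dL or more. Item 9 exempts anemia from the requirement that earlier treatment toxicity has resolved.

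The SAP does set a baseline condition for adverse events, in 7.5.2: "Treatment-emergent AEs (TEAEs) are defined as AEs started or worsened on or after first dose and will be tabulated". There it also tabulates by worst grade and counts a repeated event once at its maximum grade.

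**The concern.** Protocol 6.1 puts laboratory data in the primary tolerability endpoint, and SAP 5.2.2 lists changes in laboratory results after treatment as a safety endpoint. A proportion out of range measures prevalence, not change. The expansion cohorts have no control arm in which entry prevalence would cancel out, so each patient's own baseline is the only reference.

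The gap matters most for the liver. Protocol 10.8.1.1 names liver function test elevation as the most frequent related Grade 3/4 event with CB-839 monotherapy, and AST and ALT have the widest entry allowance. A patient who enters with ALT at 2.4 times ULN and never changes would count as abnormal on a literal reading, and so would a patient who rose to that level from normal. Two programmers could also build different tables from the same sentence.

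**Working it through.** The plan states no figure to reproduce. The check is a reading of the text, followed by an illustration on assumed rates.

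**1. Can patients be out of range at baseline?** Yes, under Protocol 6.4 items 6 and 9, as set out above.

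**2. How severe can an entry abnormality be?** Compare the entry limits with the lowest action tiers in Protocol Table 10.8-1:
- AST/ALT: entry up to 2.5 times ULN; lowest tier above 3 times ULN.
- Total bilirubin: entry up to 1.5 times ULN, apart from the Gilbert exception; lowest tier above 1.5 times ULN.
- Creatinine: entry up to 1.5 times ULN; lowest tier above 1.5 times ULN.

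For these tests the mixing therefore concerns mainly mild values.

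**3. Do the adverse event tables supply the missing count?** In part. Protocol 17.1 records a treatment-emergent laboratory abnormality as an adverse event if it brings symptoms, changes study medication or changes concomitant therapy. Those events reach the SAP 7.5.2 tables with a baseline reference and a worst grade. A rise in grade with no symptoms and no action need not become an adverse event, so no planned table has to count it as a worsening.

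**4. Does mean change supply it?** No. It uses baseline but gives no number of patients who worsened. One patient of 20 rising by 10 times ULN moves the mean by 10/20 = 0.5 times ULN.

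**5. Illustration of the mixing.** Let b be the share out of range at baseline, assumed to stay out of range without worsening, and e the new-onset rate among those in range at baseline. The documents give neither. The ranges b = 10% to 40% and e = 10% to 20% are assumptions.
- Proportion ever out of range = b + (1 − b)e
- New-onset proportion of all patients = (1 − b)e
- Difference = b
- Pre-existing share of those counted = b / [b + (1 − b)e]

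| b | e | Ever out of range | New onset | Pre-existing share |
|---|---|---|---|---|
| 10% | 10% | 19% | 9% | 53% |
| 10% | 20% | 28% | 18% | 36% |
| 20% | 10% | 28% | 8% | 71% |
| 20% | 20% | 36% | 16% | 56% |
| 40% | 10% | 46% | 6% | 87% |
| 40% | 20% | 52% | 12% | 77% |

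With 75 patients, b = 20% and e = 10%, 15 are abnormal at entry and 0.10 × 60 = 6 become abnormal: 21 counted, 6 of them new. Rows 2 and 3 both report 28%, with new onset of 18% and 8%. The same table entry can therefore stand for quite different on-treatment rates.

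**The case against.** The strongest reply is that the SAP is silent here rather than wrong. A reader might infer that the plan reports pre-existing abnormalities as if they arose on treatment. The text does not support that: 7.5.3 neither calls the summary treatment-emergent nor attributes it to drug, and a by-visit display with a baseline column would fit the sentence. This stands, and limits the point to a gap in specification. Even that display would show only net prevalence by visit: 20% at baseline and 20% later could mean that nobody changed, or that one fifth recovered while another fifth became abnormal.

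A reader might also infer that mean change is the only summary tied to baseline and would hide an individual liver signal. That goes too far. Protocol 16.1 requires minimum and maximum values and listings of all data, so a rise of 10 times ULN would be visible. Such a value also exceeds the 5 times ULN tier in Table 10.8-1, where the guideline alters both study drugs; if followed, that would meet the adverse event recording condition in Protocol 17.1. Clinically significant changes thus have their own route, tied to baseline. What these routes omit is a count of patients whose laboratory grade worsened without symptoms or action.

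Finally, the illustration is not evidence of actual inflation. That is correct.

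**Conclusion.** The point holds as a minor gap in specification. The graded laboratory summary in SAP 7.5.3 has no baseline condition, eligibility admits out-of-range values, and the adverse event tables cover only clinically significant laboratory changes. In single-arm cohorts the summary therefore cannot tell pre-existing abnormalities from new or worsened ones.

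The size is unknown. Under the assumed rates the excess equals the baseline-abnormal share, 10 to 40 percentage points, and pre-existing cases make up 36% to 87% of those counted. This rests on baseline abnormalities persisting without worsening. Grading protects the upper end for AST and ALT, since the entry ceiling lies below the first action tier. This is a descriptive safety table: ORR, alpha, power, sample size and the two-stage decision rules do not depend on it.

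**What to change.** In SAP 7.5.3:
- Add, by cohort, a shift table of baseline grade by worst post-baseline grade for each graded test, using the baseline already defined there. State the post-baseline window and include a category for missing baseline or post-baseline values.
- Define a treatment-emergent laboratory abnormality as one that is new or at least one grade worse than baseline. Report the count and proportion on that definition, including post-baseline Grade 3-4 counts.
- Keep the out-of-range proportions if wished, provided baseline is shown alongside. They need not be replaced.

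This brings laboratory reporting into line with the started-or-worsened rule in SAP 7.5.2. The cost is a few lines of SAP text and one standard table layout; no new data are needed.

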### **7.5.4 ECG and Vital Signs**

Electrocardiogram (ECG), weight, and vital signs will be summarized by changes from baseline to scheduled time points using descriptive statistics. Baseline is defined the same way as for laboratory measurements.

## **7.6 Missing Data**

Patients with missing response assessment will be treated as non-responders in analyzing ORR. Table 3 will be followed to censor these patients in analyzing PFS and DOR. Missing laboratory, ECG and vital sign measurements will not be imputed and included in the analysis. AEs with missing or partial start date that cannot be definitively determined to be earlier than first dose will be treated as TEAE. AEs with missing relationship to study treatments will be treated as related.

## **7.7 Changes in the Conduct of the Study or Planned Analyses**

The SAP version 2.0 is amended from version 1.0 to remove restriction on the primary end point for Cohort 4 so that Cohort 4 is investigator assessed, rather than IRC assessed. That is, the primary end point for Cohort 4 is the same as the other cohorts. This decision was made by the sponsor Calithera.

SAP version 2.0 also removes references to Cohort 6 because this cohort was never enrolled.

SAP version 2.0 does not require the summarization of protocol deviations because protocol deviations may not be sufficiently standardized to allow for summarization. Though referenced in the study protocol, no iRECIST analyses are to be conducted per the SAP.

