## **5.2 Study Endpoints**

### **5.2.1 Efficacy Endpoints**

#### **5.2.1.1 Primary Efficacy Endpoint**

The primary efficacy endpoint is the confirmed overall response rate (ORR) and duration of response (DOR) of patients treated with CB-839 in combination with nivolumab. Overall Response Rate is defined as the percentage of patients with complete response (CR) or partial response (PR) per Response Evaluation Criteria in Solid Tumors (RECIST) v1.1. DOR is defined as the time between the first

documentation of a PR or a CR per RECIST v1.1 to the first documentation of progressive disease (PD) or death. For all cohorts, the primary end point is investigator assessed.

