**Table 1 Summary of Sample Size and Power for Expansion Cohorts**

Cohort	p0 (Background ORR (%))	p1 (Target ORR (%))	A	Power (%)	n1 for Stage 1 (r1)	n2 (n - n1) for Stage 2	Total n (r2)
1	25%	40%	0.1	80	25 (7)	27	52 (16)
2	5%	15%	0.1	80	20 (1)	36	56 (4)
3	5%	20%	0.1	80	9 (0)	15	24 (2)
4	5%	20%	0.1	80	9 (0)**	66	75 (13)
5	5%	15%	0.1	80	20 (1)	36	56 (4)
6	5%	20%	0.1	80	9 (0)	15	24 (2)

\*For all cohorts, false positive rate ( $\alpha$ ) = 0.1

\*\*Completed prior to protocol Amendment 2 expansion of cohort

### Expanded Cohort 4

A multi-stage design will be used as a guide for the melanoma expansion cohort 4 to decide whether the treatment of CB-839 in combination with nivolumab warrants more extensive development in this population. At first, a Simon 2-stage design ([Table 1](#)) with a reasonable false positive rate (eg, FPR < 10%) and false negative rate (eg, FNR < 20%) was used for the decision making based on assumptions of target (20%) and background (5%) response rate. Following a positive result in the initial two stage design and preliminary evidence of a treatment effect that may represent substantial improvement over available therapies, approximately 75 subjects in total will be treated in Cohort 4. The sample size at this expanded stage is determined based on the ability to produce a confidence interval (CI) that would exclude the historic response rate (assumed to be 10%) and to provide sufficient information for a reliable understanding of the safety profile. Specifically, the lower limit of the 95% CI associated with observation of an objective response rate of 18.7% in 75 treated subjects (14/75 responders) excludes 10%. Interim clinical monitoring will be performed in this expansion to ensure adequate safety and tolerability as well as favorable risk/benefit by assessing preliminary efficacy measures such as objective response rate and duration of response.

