### **7.4.1 Primary Analysis of Overall Response Rate**

Overall Response Rate (ORR) will be assessed by cohort where ORR is defined as the percentage of patients with complete response (CR) or partial response (PR) per Response Evaluation Criteria in Solid Tumors (RECIST) v1.1. To be assigned a status of CR or PR, changes in tumor measurements must be confirmed by repeat assessment performed no less than 4 weeks after the criteria for response were first met. Patients without assessed response will be treated as non-responders.

The analysis set for ORR will be the response evaluable analysis set. An estimate of ORR and its 95% CI will be calculated with the Clopper-Pearson method. Best Overall Response (BOR) Rate is defined as the percentage of patients with their best of response being will be estimated in the same approach as for ORR.

Duration of Response (DOR): For patients achieving a PR or a CR, the duration of response will be calculated as the time between the first documentation of a PR or a CR to the first documentation of PD or death, whichever occurs first. For patients achieving first a PR then a CR, the PR date will be the starting date for response duration calculation. Patients who are alive and have not experienced disease progression at the time of the analysis will follow the censoring rules in [Table 2](#) where only assessments after first response will be included. The determination of DOR is based on responders only.

Kaplan-Meier methodology will be used to estimate median DOR for each cohort and construct survival curves for visual description. The Brookmeyer-Crowley methodology will be used to construct the 95% CI for the median DOR for each cohort (2). DOR will be analyzed using response evaluable analysis set.

DOR will be reported for patients with confirmed OR.

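### SAP version 2.0 drops the protocol's IRC-assessed Cohort 4 primary endpoint, gives no reason beyond a sponsor decision, and specifies no IRC or concordance analysis

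*SAP*

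**What the plan says.** **Protocol Amendment 2.** Sections 6.3.2.4, 6.6 and 16.5 each make IRC assessment the basis of the Cohort 4 primary endpoints, ORR and DOR. Sections 6.6 and 16.5 expressly except Cohort 4 from the investigator assessment used elsewhere. Section 16.2 sets up an IRC for Cohort 4 alone. The objectives table in 6.1 is broader: it lists an investigator-assessed primary covering all three tumor types, melanoma included, and a separate IRC-assessed primary for melanoma.

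**SAP version 2.0.** Section 5.1 refers the reader to Amendment 2. Section 5.2.1.1 states: "For all cohorts, the primary end point is investigator assessed". Section 7.4 and the progression row of Table 2 follow the same line. Section 7.7 records that version 2.0 was amended to "remove restriction on the primary end point for Cohort 4 so that Cohort 4 is investigator assessed, rather than IRC assessed". The explanation offered is "This decision was made by the sponsor"; the remark that Cohort 4 now matches the other cohorts describes the effect and is not a reason.

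**Sizing.** Section 5.3 still justifies about 75 patients by the statement that the lower 95% limit for an "objective response rate of 18.7% in 75 treated subjects (14/75 responders) excludes 10" per cent, the assumed historic rate. It introduces the design with "A multi-stage design will be used as a guide for the melanoma expansion cohort 4". On method, 7.4.1 says: "An estimate of ORR and its 95% CI will be calculated with the Clopper-Pearson method".

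**The concern.** Cohort 4 is open-label and single-arm, so there is no concurrent control against which reader differences could cancel. Who calls a response, and who dates progression for DOR, bears directly on what the cohort can show. Amendment 2's stated rationale linked the IRC objective to the enlargement to about 75 patients. The SAP keeps the enlargement and removes the assessor that came with it.

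Following the SAP therefore gives a Cohort 4 primary result that is not the one protocol 6.3.2.4, 6.6 and 16.5 define. With no IRC table and no concordance table, a reader of the report could not tell whether an independent read agrees. Section 7.7 also does not say which Cohort 4 response data were known when the decision was taken. That would be a normal statement to make, because section 5.3 provides for interim monitoring by "assessing preliminary efficacy measures such as objective response rate and duration of response".

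**Working it through.** **Step 1: the two documents side by side.**

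| Point | Protocol Amendment 2 | SAP version 2.0 |
|---|---|---|
| Assessor, Cohort 4 primary ORR and DOR | IRC (6.3.2.4, 6.6, 16.5) | Investigator (5.2.1.1, 7.4, Table 2) |
| Melanoma primaries in the objectives table | Investigator and IRC (6.1) | Investigator only |
| IRC for Cohort 4 | To be established (16.2) | Only in the abbreviation list and in 7.7 |
| Confirmation at 4 weeks or more | Yes (16.5) | Yes (7.4.1) |
| Sizing | About 75, 14 responders, 10% (16.3) | Same (5.3) |
| Reason for the change | – | Sponsor decision (7.7) |

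Confirmation, sizing and the historic rate agree. The assessor does not, and no IRC-assessed or concordance analysis is specified. Pages have been removed from the public SAP. However, the endpoint and methods sections where such an analysis would stand (5.2, 7.4) are present, and the contents list shows nothing after Appendix A.

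**Step 2: reproduce the SAP's own figure.** The inputs are n = 75, x = 14, a historic rate of 10% (5.3) and the Clopper-Pearson 95% interval (7.4.1).

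Lower limit = 2.5% quantile of Beta(x, n − x + 1); upper limit = 97.5% quantile of Beta(x + 1, n − x).

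For x = 14: 14/75 = 18.67%. Beta(14, 62) gives a lower limit of 10.60% and Beta(15, 61) an upper limit of 29.33%. 10% is excluded, as stated.

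**Step 3: move the count by one.** For x = 13: 13/75 = 17.33%, with an interval of 9.57% to 27.81%. 10% is not excluded. So if investigators count 14 and the IRC upholds one fewer net, the exclusion is lost; if investigators count 13 and the IRC adds one net, it is gained.

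**Step 4: vary n, since the plan says approximately 75.**

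| n | Lower limit, 13 responders | Lower limit, 14 responders | Smallest count excluding 10% |
|---|---|---|---|
| 71 | 10.13% | 11.22% | 13 |
| 72 | 9.98% | 11.06% | 14 |
| 75 | 9.57% | 10.60% | 14 |
| 78 | 9.18% | 10.17% | 14 |

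The smallest count is 13 for every n from 65 to 71 and 14 for every n from 72 to 78. The boundary moves with n, but a one-response boundary exists at each n.

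**Step 5: the 5% background rate in SAP Table 1.** 9/75 has a lower limit of 5.64% and 8/75 of 4.72%. A one-response difference near 14 leaves the exclusion of 5% untouched; only the 10% benchmark is sensitive there.

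**The case against.** The sponsor has a fair reply on several points, and parts of it stand.

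- **Investigator assessment is already a listed primary for melanoma (protocol 6.1).** This stands. The SAP has not invented an endpoint; it has dropped one of two. It does not settle the matter, because the three Cohort 4-specific sections are unambiguous.
- **The change is disclosed.** This stands. Section 7.7 names the old assessor, the new one and who decided, so there is no concealment. What is missing is the reason, the date, the data known and the IRC analysis.
- **Scans are still centrally collected.** Protocol 10.3 and SAP Appendix A footnote 12 send them to a reader for exploratory use. It would be wrong to say that no independent reading remains. But that reader is not described as the IRC, and the SAP specifies no analysis of those reads.
- **The numerical point is built in.** Any minimum count has a neighbor that fails. This stands: the sensitivity matters only if the observed count falls next to the boundary. Actual Cohort 4 enrollment is not given, the Cohort 4 text calls the design a guide, and 7.4.1 plans only an estimate and its interval.

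A reader might also infer that the assessor was changed because Cohort 4 results had been seen, pointing to the remark in 7.7 that Cohort 6 is removed because "this cohort was never enrolled". The documents do not support this. The remark dates nothing about Cohort 4 data. Investigator responses in an open-label cohort are always visible: the amendment that introduced the IRC itself reports 3 responders in 16. Nothing shows that IRC results existed or were looked at.

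**Conclusion.** The point holds in this form. For Cohort 4, the SAP's primary analysis is not the one its governing protocol sections define. The change is disclosed but not justified, and the plan offers no means of comparing investigator and IRC reads.

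The size can be shown only at the boundary: at n = 75, one net response separates a lower limit of 10.6% from 9.6% against 10%. This assumes 75 evaluable patients and the SAP's own interval. The documents give no IRC-investigator discordance rate, so neither the size nor the direction of any difference is estimated. It could raise or lower the ORR. A reader might conclude that investigator assessment inflates the Cohort 4 ORR, or that 14/75 is a formal success rule that is now compromised. The documents establish neither.

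The documents also do not show whether the IRC reads were carried out, so the remedy has two branches.

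**What to change.** **If IRC reads exist.** In SAP 5.2.1.1 and 7.4, report IRC-assessed confirmed ORR and DOR as the Cohort 4 primary. In Table 2, apply IRC progression dates to Cohort 4 DOR only; that table also governs PFS and the other cohorts, which should stay unchanged. Show the investigator results and an IRC-investigator concordance table alongside.

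**If they do not exist.** In SAP 7.7 and the report, state why, when the decision was taken and which Cohort 4 data were then known. Label the investigator-assessed result as a departure from the protocol's Cohort 4 primary endpoint. Do not present it as an independently confirmed exclusion of 10%.

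**In both cases.** Record in SAP 7.7 how protocol 6.1 is read alongside 6.3.2.4, 6.6 and 16.5. The protocol text itself can wait for a next amendment.

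**Cost.** In the first case, programming of the IRC tables and one concordance table; in the second, text only. No new reads are requested. The drawback is that the two reads may give different ORRs, which the report would then have to explain.
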